Observational cohort study of blood transcriptomics and proteomics information as biomarkers of traumatic encephalopathy syndrome

Version: 1.0

Date: June 10th, 2021

Organization Committee

Tianjin Medical University General hospital

Contents

Protocol Abstract	3
1. Background and objective of the study	5
2. Study design	7
2.1 Overall design	7
2.2 Estimated number of subjects	7
3. Screening, Inclusion, Exclusion and Withdrawal Criteria	7
3.1 Athletes and Patients with TBI.....	7
3.2 Healthy Volunteers	8
4. Study procedure	8
4.1 Screening assessment	9
4.2 Included subjects	9
5. Evaluation parameters	9
5.1 Primary outcome parameters	9
5.2 Secondary outcome parameters	9
6. Withdrawal of the subject	10
7. Trial management	10
7.1 Ethics	10
7.2 Informed consent and data protection agreement	10
7.3 Withdraw from the trial	11
7.4 Subjects privacy	11
7.5 Modification of the trial protocol	11
7.6 Original records certification	11
7.7 Documents on file	12
7.8 Quality control	12
8. References	12

Protocol Abstract

Title	Observational cohort study of blood transcriptomics and proteomics information as biomarkers of traumatic encephalopathy syndrome
Ethics Committee (Grant Number)	The ethics committee of Tianjin Medical University General Hospital (IRB2021-YX-056-01)
Principal Investigator	[name] (Ph.D.), [name] (M.D.)
Sponsor	Tianjin Medical University General Hospital
Fundings	Natural Science Foundation of China (Grant No. 82071394, 82072166)
Execute Time	05/01/2021-11/01/2022
Recruiting Time	05/01/2021-11/01/2022
Objective	Create a novel set of CTE/TES molecular diagnostic signatures to open a new avenue of clinical diagnosis of the disease and future research on the therapeutic strategy
Study Type	Observational
Enrollment	120 participants
Biospecimen	Description: Serum Retention: Samples with DNA
Sampling Method	Non-probability sample (invitation to volunteer)
Condition	Chronic Traumatic Encephalopathy (CTE) / Traumatic Encephalopathy Syndrome (TES)
Study Groups/Cohorts	1) 50 active or retired athletes from the Weightlifting, Wrestling, Judo, Boxing and Taekwondo Sports Management Center of Tianjin Sports Bureau. 2) 50 patients with multiple (≥ 2 times) exposure to brain trauma attending Tianjin Medical Insurance designated hospitals such as Tianjin Medical University General Hospital. 3) 20 healthy volunteers.
Screening Criteria	1. Athletes and patients with traumatic brain injury 1) Age ≥ 18 and ≤ 80 years old with independent behavior ability or authorized legal representative. 2) Have a clear history of repetitive mild TBI, concussion or subconcussion. 3) The most recent head injury occurred 3 months ago. 2. Healthy Volunteers 1) Age ≥ 18 and ≤ 80 years old with independent behavior ability. 2) No history of repetitive mild TBI, concussion or subconcussion.

	3) Fully understands the nature of the study, and voluntarily participates and signs the informed consent.
Inclusion Criteria	On the basis of meeting the screening criteria, the participants need to fully understand the nature of the study, and sign the informed consent form.
Exclusion Criteria	
1. Athletes and patients with traumatic brain injury
 
1) Pregnant or lactating women.
 
2) History of other neurological diseases.
 
3) History of tumors, hematological diseases, severe cardiopulmonary diseases, hepatic failure or renal failure.
 
4) Have participated in clinical trials in the past four weeks.
 
5) The investigator believes that not appropriate for inclusion.
 
2. Healthy Volunteers
 
1) Pregnant or lactating women.
 
2) History of TBI or other neurological diseases.
 
3) History of tumors, hematological diseases, severe cardiopulmonary diseases, hepatic failure or renal failure.
 
4) Have participated in clinical trials in the past four weeks.
 
5) The investigator believe that not appropriate for inclusion.

Outcome Measures	
1. Blood tests (30-ml venous blood) for the following items.
 
1) Transcriptomics and proteomics high-throughput detection and quantitative verification;
 
2) Exosomal transcriptomics and proteomics high-throughput detection and quantitative verification;
 
3) Quantitative detection for classical biomarkers of traumatic brain injury, including S100B, GFAP, UCH-L1, NFL, T-Tau and p-Tau181.
 
2. Cognitive function tests, including RPQ, MMSE and MoCA.
 
3. Possible head MRI (plain scan and DTI sequence) examination and head PET (FDG-PET, Tau-PET and Amyloid-PET) examination

Reference standard	Clinical Approach to the Diagnosis of TES (Reams N., JAMA Neurology, 2016)
Statistical Analysis	
All statistical analyses were performed using Stata/MP Version 14.0 (Stata Corp., College Station, TX, USA) and PASW Stastics Version 18.0 (IBM, Armonk, NY, USA).
 
A two-tailed p value of less than 0.05 was considered to be statistically significant.

1. Background and objective of the study

Chronic traumatic encephalopathy (CTE) is a distinct neurodegenerative disease associated with traumatic brain injury (TBI). It is characterized by the clinical manifestations of progressive cognitive and neurological dysfunction, and the pathological changes of abnormal deposition of phosphorylated tau protein in neurons, astroglia and synapses around small blood vessels at the depths of cortical sulci. The occurrence of the disease is closely related to a history of repetitive mild TBI, concussion and sub-concussion, so that it is susceptible in boxers and other contact sports athletes, military veterans, elderly people with mobility impairments and victims of domestic violence.

The clinical symptoms of CTE mainly include cognitive decline, behavioral change, emotional dysregulation and motor disturbance. The cognitive decline typically affects more than one domain of neurological deficits including executive, visuospatial, memory and language. Patients with mainly behavioral change may exhibit violence, poor impulse control, socially inappropriate behavior, avolition, apathy, change in personality and comorbid substance abuse. The emotional dysregulation includes depression, anxiety, agitation, aggression, paranoid ideation, deterioration of interpersonal relationships and suicidality, while the motor disturbance contains bradykinesia, tremor, rigidity, gait instability, dysarthria, dysphagia, ataxia and gaze disturbance. From this, **CTE can seriously influence the quality of life. Consequently, early diagnosis and treatment for the disease has important clinical significance.**

The traditional diagnostic criteria of CTE are based on neuropathology, which causes most patients to be diagnosed only by autopsy. In order to develop a clinical diagnostic criterion of CTE, so that the patients could receive effective treatment in time, the concept of Traumatic Encephalopathy Syndrome (TES) was proposed. Specifically, potential patients with CTE are divided into three categories: probable TES, possible TES and unlikely TES according to the likelihood of illness. The classification is based on the number of head traumas, clinical features and progressive courses. **This diagnostic framework of TES provides a practical approach for clinical evaluation of CTE.**

However, the diagnostic criteria of CTE and TES that are based solely on clinical symptoms still lack sufficient specificity and sensitivity, while biomarkers could be an important aid to fill the deficiency and further improve diagnosis level of the disease. Blood biomarkers have always been a research hotspot in the field of neurotrauma due to their easy access to specimens and convenience

for detection. In recent years, many researches have shown that protein biomarkers including S100B, GFAP, UCH-L1, NFL, T-Tau and p-Tau181 could have diagnostic value in mild TBI and cognitive dysfunction of chronic TBI. However, these researches are not special study on CTE and TES, and are limited by the research design (such as small sample size without high-throughput screening). In addition, because of the incompatibility (low sensitivity or reproducibility) of clinical examination platform, only S100B (with a dedicated Elecsys-Roche testing platform) from the above biomarkers has been applied in clinical auxiliary diagnosis of mild TBI till now. Therefore, **further exploration of new biomarkers for CTE/TES that can contribute to clinical diagnosis has great application value.**

Recently, with the development of molecular biology and bioinformatics, the potential value of transcriptomic information (including mRNA, miRNA, lncRNA, circRNA, etc.) as disease biomarkers has aroused wide attention. For clinical blood samples, the RNA detection method (RT-PCR) is mature with the advantage of high specificity and reproducibility. It is a same commonly used clinical testing technique as protein detection. Exosomes are small vesicles secreted by living cells into the extracellular space that function as important carriers of information transferred among cells. They contain a large number of specific proteins and functional nucleic acids, participate in many pathophysiological processes, and correlated with the occurrence and progression of many diseases. Because the membrane structure of exosomes can protect their internal RNA from RNase degradation, exosomal RNA is more stable and has higher concentration than free RNA in serum or plasma. In addition, in view of the maturity of the isolation and purification technology for exosomes (a large number of assay kits have been used in clinical examination and scientific research), exosomal protein and RNA have been regarded as an important source of clinical biomarkers. Consequently, **exploring exosomal diagnostic biomarkers for CTE/TES would be a breakthrough point to solve the problem of early diagnosis of the disease.**

In this study, we will use high-throughput screening and multi-omics (transcriptomics and proteomics) joint analysis technology to explore potential CTE/TES biomarkers (RNA and protein) in blood and its exosomes. We will also combine them with the reported TBI biomarkers to **create a novel set of CTE/TES molecular diagnostic signatures, in order to open a new avenue of the clinical diagnosis of the disease and the future research on its therapeutic strategy.**

2. Study design

2.1 Overall design

This project is an observational cohort study.

2.2 Estimated number of subjects

Estimated by statistical analysis, 70 subjects are expected to take part in this study, including 30 active or retired athletes from the Weightlifting, Wrestling, Judo, Boxing and Taekwondo Sports Management Center of Tianjin Sports Bureau, 30 patients with multiple (≥ 2 times) exposure to brain trauma attending Tianjin Medical Insurance designated hospitals such as Tianjin Medical University General Hospital, and 10 healthy volunteers.

3. Screening, Inclusion, Exclusion and Withdrawal Criteria

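### The protocol states two planned sample sizes for the same three groups: 120 (50/50/20) in the abstract and 70 (30/30/10) in Section 2.2

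*Protocol*

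**What the plan says.** The Protocol Abstract gives the size in two rows. Under Enrollment it has "120 participants". Under Study Groups/Cohorts it splits these into "50 active or retired athletes from the Weightlifting, Wrestling, Judo, Boxing and Taekwondo Sports Management Center", "50 patients with multiple (≥ 2 times) exposure to brain trauma attending Tianjin Medical Insurance designated hospitals" and "3) 20 healthy volunteers".

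Section 2.2 (Estimated number of subjects) says "Estimated by statistical analysis, 70 subjects are expected to take part in this study, including 30 active or retired athletes", followed by "30 patients with multiple (≥ 2 times) exposure to brain trauma attending Tianjin Medical Insurance designated hospitals" "and 10 healthy volunteers".

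The athletes and the patients are described in the same terms and come from the same sources in both places; only the counts change. Both statements are current text of Version 1.0, and the document has no amendment log.

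Two other entries bear on the matter. The abstract gives the sampling method as "Non-probability sample (invitation to volunteer"). Section 6 sets a 20% ceiling on loss and says that withdrawn subjects are not replaced.

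**The concern.** The planned number of participants is a basic design figure, and here it has two values, in total and in every group. The text does not show which one is meant. Section 2.2 attributes 70 to a statistical estimate. The abstract puts 120 first and does not tie it to any such estimate. A reader cannot tell which number the calculation supports.

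The consequence is loss of control over the size of the study. A final enrollment near 70 or near 120 could each be presented as the plan. Section 7.5 has the ethics committee approve the protocol before the start, and Section 7.8 lets the sponsor and the medical administration review whether the study runs as laid down. On sample size, neither has a single figure to apply.

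**Working it through.** **Inputs.** Abstract: total 120; groups 50, 50, 20. Section 2.2: total 70; groups 30, 30, 10. Section 6: loss at most 20%, no replacement.

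**1. Does each total match its own groups?**
- Abstract: 50 + 50 + 20 = 120.
- Section 2.2: 30 + 30 + 10 = 70.

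Both agree, so neither an addition error nor a single misread digit explains the difference. Beyond these sums neither total can be reproduced, because the protocol gives no effect size, variability, power or target accuracy. Those may be in the SAP, and their absence is not part of this point.

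**2. Size of the gap.**

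| | Abstract | Section 2.2 | Difference |
|---|---|---|---|
| Athletes | 50 | 30 | 20 |
| Patients | 50 | 30 | 20 |
| Healthy volunteers | 20 | 10 | 10 |
| Total | 120 | 70 | 50 |

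120/70 - 1 = 71.4%, and 1 - 70/120 = 41.7%. The exposed-to-healthy ratio is 100:20 = 5:1 in the abstract and 60:10 = 6:1 in Section 2.2, so one set is not a scaled copy of the other.

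**3. Could 70 be the number left after loss, and 120 the number recruited?**
- Inflating 70 for 20% loss: 70/(1 - 0.20) = 87.5, so 88. The cruder 70 x 1.2 gives 84. Neither is 120.
- By group: 30/0.8 = 37.5, not 50; 10/0.8 = 12.5, not 20.
- Applying 20% loss to 120: 120 x 0.8 = 96 (40/40/16), not 70.
- Loss needed to go from 120 to 70: 41.7% overall, 1 - 30/50 = 40% in each exposed group and 1 - 10/20 = 50% in the healthy group. That is about twice the ceiling or more.

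**4. Fewest completers if the ceiling is just met.** 120 x 0.8 = 96 (40/40/16), or 70 x 0.8 = 56 (24/24/8).

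**5. Effect on precision (illustration only).** Assume a comparison of two group means with equal SD; the protocol does not specify this analysis. The standard error is proportional to sqrt(1/n1 + 1/n2). Smaller plan over larger plan:
- Athletes vs patients: sqrt(2/30)/sqrt(2/50) = 0.2582/0.2000 = 1.291.
- One exposed group vs healthy: sqrt(1/30 + 1/10)/sqrt(1/50 + 1/20) = 0.3651/0.2646 = 1.380.
- Both exposed groups vs healthy: sqrt(1/60 + 1/10)/sqrt(1/100 + 1/20) = 0.3416/0.2449 = 1.394.

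**The case against.** The best rescue is that the two figures describe different things. Three versions were considered.

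- **Stage or subset.** Section 5.1 has markers screened by high-throughput methods and then verified, so 70 might be one of these steps. But Section 4.2 lists both steps for all included subjects, and no section ties 70 to either. Imaging is limited to those eligible, but no number is given for it.
- **Invited versus enrolled.** Recruitment is by invitation, so 120 might be the number approached. But 120 stands under Enrollment, and the invitation wording belongs to the sampling method.
- **Left to the SAP.** An SAP may hold the calculation. It could justify one figure, but it cannot make two current protocol statements agree.

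Some of the other side does stand. The 20% in Section 6 is a ceiling and not an expected loss, so 96 and 56 are lower bounds and not forecasts. Section 4.2 schedules no repeat visit, so loss may matter little. The precision figures rest on an assumed comparison; the contrast of interest may instead be by clinical TES status. The study is observational with a volunteer sample, and the text ties no power claim or decision rule to either total, so a specific statistical harm is not shown. Section 7.8 grants authority to review; it does not require a check of enrollment against target. None of this removes the contradiction.

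**Conclusion.** The concern holds. Version 1.0 gives two incompatible planned sizes, 120 and 70, which differ by 50 participants in total and in all three groups. The conclusion rests only on the counts as printed and on the absence of any text linking them. It needs no assumption about the analysis. The one quantitative link the document offers, the 20% loss ceiling, fails by a wide margin (41.7% would be needed).

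The standard error would be about 29% to 39% larger under the smaller plan, but only on the assumed comparison of means, and the finding does not depend on it. The protocol does not show which figure is intended. This must be corrected, because the enrollment target is indeterminate as written.

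**What to change.** State one total and one set of group sizes, identical in the abstract and in Section 2.2. If 70 is kept, change the Enrollment and Study Groups/Cohorts rows of the abstract. If 120 is kept, change Section 2.2. Keep the reference to a statistical estimate only if the calculation supports the retained figure. It would help, though it is not essential, to say whether the number is those enrolled or those expected to complete, given the ceiling and the no-replacement rule in Section 6.

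The edit itself is small. The procedural cost is larger: during the study, Section 7.5 sends a modification to the principal investigator and the sponsor, then to the ethics committee, and says research resumes only after re-approval, which implies a pause. One of the two stated targets is withdrawn; if the smaller is kept, stated enrollment falls from 120 to 70. Whether recruitment itself must change depends on which figure is kept, and the protocol does not settle that.

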3.1 Athletes and Patients with TBI

Screening Criteria

- 1) Age ≥ 18 and ≤ 80 years old with independent behavior ability or authorized legal representative.
- 2) Have a clear history of repetitive mild TBI, concussion or subconcussion.
- 3) The most recent head injury occurred 3 months ago.

Inclusion Criteria

On the basis of meeting the screening criteria, the participants need to fully understand the nature of the study, and voluntarily participate in the study and sign the informed consent form.

Exclusion Criteria

- 1) Pregnant or lactating women.
- 2) History of other neurological diseases.
- 3) History of tumors, hematological diseases, severe cardiopulmonary diseases, hepatic failure or renal failure.
- 4) Have participated in clinical trials in the past four weeks.
- 5) The investigator believe that not appropriate for inclusion.

Withdrawal criteria

The subject is considered as withdrawal if he/she could not complete the trial for following reasons:

- 1) The subject decides to withdraw from the study.
- 2) Lost to follow-up.
- 3) The doctor or the researcher asks the subject to withdraw from the study (e.g. poor compliance).

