3.2 Healthy Volunteers

Screening Criteria

- 1) Age \geq 18 and \leq 80 years old with independent behavior ability.
- 2) No history of repetitive mild TBI, concussion or subconcussion.
- 3) Fully understands the nature of the study, and voluntarily participates and signs the informed consent.

Inclusion Criteria

On the basis of meeting the screening criteria, the healthy volunteers need to fully understand the nature of the study, and sign the informed consent form.

Exclusion Criteria

- 1) Pregnant or lactating women.
- 2) History of TBI or other neurological diseases.
- 3) History of tumors, hematological diseases, severe cardiopulmonary diseases, hepatic failure or renal failure.
- 4) Have participated in clinical trials in the past four weeks.
- 5) The investigator believes that not appropriate for inclusion.

Withdrawal criteria

The subject is considered as withdrawal if he/she could not complete the trial for following reasons:

- 1) The subject decides to withdraw from the study.
- 2) Lost to follow-up.
- 3) The doctor or the researcher asks the subject to withdraw from the study (e.g. poor compliance).

4. Study procedure

Researchers initiate the study according to enrolled order after verification of the inclusion/exclusion criteria and collection of the informed consent.

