4.1 Screening assessment

Researchers should clearly evaluate each inclusion and exclusion criteria for the subjects. The following works need to be done during screening:

- 1) Filling general information, such as date of birth, gender, occupation, et al.
- 2) Medical history collection: History of head injuries (number, degree, time, et al.), past medical history, et al.
- 3) Basic physical examination.

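### Does the 3-month injury interval in screening criterion 3 need correcting because it lacks a direction and a reference date?

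*Protocol*

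**What the plan says.** Section 3.1 of the Protocol sets three screening criteria for athletes and patients with TBI. The second is "Have a clear history of repetitive mild TBI, concussion or subconcussion". The third is, in full, "The most recent head injury occurred 3 months ago". The Abstract carries the third in the same words.

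Other limits in Section 3.1 do have a direction. Age is bounded with inequality signs on both sides, and an exclusion reads "Have participated in clinical trials in the past four weeks".

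The criterion applies to two groups. The Abstract plans "50 active or retired athletes from the Weightlifting, Wrestling, Judo, Boxing and Taekwondo Sports Management Center of Tianjin Sports Bureau" and 50 patients with at least two brain traumas. Section 2.2 plans "30 active or retired athletes from the Weightlifting, Wrestling, Judo, Boxing and Taekwondo Sports Management Center of Tianjin Sports Bureau" and 30 such patients. The two sets of numbers disagree, which is a separate matter; both are carried below. The Abstract gives the recruiting time as "05/01/2021-11/01/2022".

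Healthy volunteers fall under Section 3.2, which excludes anyone with "History of TBI or other neurological diseases". Section 4.1 says "Researchers should clearly evaluate each inclusion and exclusion criteria for the subjects" and has the number, severity and timing of past head injuries recorded at screening.

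**The concern.** A numeric eligibility limit without a direction can be read three ways: at least 3 months, at most 3 months, or exactly 3 months before some date. The first two select nearly complementary populations that share only the 3-month point. On the bare text, two screeners could reach opposite decisions about the same person.

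The stake would be the outcomes. Sections 5.1 and 5.2 measure blood levels of novel and classical markers, and Section 1 says that the classical ones may be informative in mild TBI as well as in chronic TBI. Apart from general investigator discretion, criterion 3 is the only limit on how recent the last injury may be. Healthy volunteers have no TBI history. If recently injured people entered the exposed groups, a signal of recent injury could therefore be mistaken for a marker of TES.

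Two smaller questions go with this: from which date the 3 months are counted, and whether a subconcussive impact, which qualifies under criterion 2, counts as a head injury under criterion 3.

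**Working it through.** The Protocol attaches no figure to this point, and no sample size, power or alpha calculation depends on it. The check is to try each reading against the rest of the Protocol.

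1. **Reach of the criterion.** By the Abstract, (50 + 50)/120 = 83.3%. By Section 2.2, (30 + 30)/70 = 85.7%. This is the share to whom the criterion applies, and so only a ceiling on the share whose eligibility turns on how it is read.

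2. **Exactly 3 months.** Each screening day would have a single qualifying injury date. Almost nobody could enter, so no screener would work this way.

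3. **At most 3 months.** With the recruitment dates read month-first, recruitment starts on 1 May 2021, and 3 months earlier is 1 February 2021. Read day-first, it starts on 5 January 2021, and 3 months earlier is 5 October 2020. Anyone last injured before that date could never qualify, and the cut-off moves later as recruitment goes on. Retired athletes could enter only with a fresh injury, yet both the Abstract and Section 2.2 invite them without such a condition. Section 1 also describes a neurodegenerative disease whose clinical classification rests partly on a progressive course, which sits badly with restricting entry to the recently injured. Where Section 3.1 does mean a recent window, as for trial participation, it uses different words.

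4. **At least 3 months.** There is no earliest injury date. Retired athletes qualify whenever they were last injured, and active athletes and patients qualify once 3 months have passed. Every group that the Protocol names can be recruited, and the disease focus is respected.

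5. **Reference date.** The sentence counts back from the time at which it is applied. It stands under the heading for screening criteria, and Section 4.1 places evaluation of the criteria at screening. The trial-participation exclusion names no reference date either, and its meaning is clear.

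6. **Confounding.** Section 4.1 records the timing of head injuries, so time since last injury can be described and examined in the analysis. The one-sided signal also presupposes a comparison of exposed with healthy participants. The Abstract names a clinical TES diagnosis as reference standard, and Section 1 describes probable, possible and unlikely categories. In a comparison of those categories among exposed participants, a recent-injury signal need not fall on one side. The Protocol does not fix which contrast is meant.

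7. **Size of any effect.** The Protocol gives no distribution of injury dates among candidates. Neither the number whose eligibility depends on the reading nor any shift in marker levels can be computed.

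**The case for a change.** The best case for a change is that eligibility belongs in the protocol and cannot be left to an analysis plan. A plausible intention is not an auditable rule, and the same section shows that its authors could write a direction when they wanted one. For hospital patients a recent-injury window is not absurd in itself. Screening and blood collection are not tied to one day, so an active athlete could be injured between them. The correction would be one line in two places.

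Part of this stands. The direction word is missing from both places, no other section supplies it, and the minimum interval remains an inference. The possible gap between screening and blood draw is also real, but adding a direction word to a criterion judged at screening would not close it.

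The rest does not carry the point. One criterion covers athletes and patients alike, so a reading that might suit some patients but shuts out most retired athletes is not workable. That two screeners would in fact disagree is possible on the bare sentence but unlikely for anyone who knows whom the study recruits. A low cost is a reason to correct something only if the correction alters what is done, and here it would write down what screeners would apply anyway. The subconcussion question is one of definition. The Protocol gives no basis for answering it either way, and investigators can settle it when they take the injury history.

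**Conclusion.** The wording gap is real, but it is a clerical omission with one workable reading, and no change to the plan follows. The missing reference date is largely supplied by the heading and by Section 4.1. The criterion applies to 83% or 86% of planned participants, depending on which enrolment figures are used; the share affected by the ambiguity cannot be computed, and no enrolment error or marker bias is shown.

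This rests on two assumptions: that screeners read the criterion in the light of the retired athletes and the chronic condition that the Protocol names, and that the timing of head injuries is recorded as Section 4.1 requires. Evidence that a screener had applied 3 months as a maximum would reopen the question.

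### Does the 3-month screening criterion leave active athletes' recent subconcussive contact unresolved in a way that calls for a change?

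*Protocol*

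**What the plan says.** For athletes and patients, Protocol Section 3.1 lists the exposure as screening criterion 2, "Have a clear history of repetitive mild TBI, concussion or subconcussion", and the timing as criterion 3, "The most recent head injury occurred 3 months ago". The Protocol Abstract repeats both. No section defines head injury or says whether a subconcussive impact is one.

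The Background (Section 1) describes the disease as "closely related to a history of repetitive mild TBI, concussion and sub-concussion, so that it is susceptible in boxers and other contact sports athletes". Healthy volunteers must meet "No history of repetitive mild TBI, concussion or subconcussion" (Section 3.2), and a separate exclusion there bars any history of TBI.

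The athlete group is "50 active or retired athletes from the Weightlifting, Wrestling, Judo, Boxing and Taekwondo Sports Management Center" in the Abstract and "30 active or retired athletes from the Weightlifting, Wrestling, Judo, Boxing and Taekwondo Sports Management Center" in Section 2.2. The screening history in Section 4.1 asks for "History of head injuries (number, degree, time, et al.), past medical history, et al", and occupation is recorded as general information. The outcomes in Sections 5.1 and 5.2 include blood levels of novel RNA and protein markers (primary) and of six classical TBI markers (secondary).

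**The concern.** The term changes between two adjacent criteria. Subconcussion is enough to enter under criterion 2, but the clock in criterion 3 runs from an undefined head injury. Two screeners could decide differently on the same active boxer.

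Take criterion 3 as a minimum interval. If subconcussion counts, an active athlete with head contact in the last 3 months is refused, although the group is described as including active athletes. If it does not count, an athlete who qualifies on subconcussion alone has no date to count from, and others may be sampled shortly after contact.

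The second case matters because the Background says the classical markers "could have diagnostic value in mild TBI and cognitive dysfunction of chronic TBI". A short-lived rise after contact could then look like a chronic difference between athletes and volunteers. If the date of last contact is not recorded, a later analysis could not adjust for it.

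**Working it through.** The protocol states no figure on this point, so there is none to reproduce. The check is of the text first, then of what the arithmetic can and cannot show.

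**Direction of the interval.** Three readings are possible: exactly 3 months, within 3 months, at least 3 months. The first would admit almost nobody. The second fits poorly with a group that includes retired athletes and with a chronic, progressive condition. A minimum interval is the reading that fits the rest of the protocol, though the text does not say so.

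**Which events count.** Criterion 3 directly follows criterion 2, so its most recent head injury can be read as the latest of the events just named. Under that reading:
- everyone admitted under criterion 2 has an event to date;
- Section 4.1 already asks for the time of that event;
- the cohort description is not contradicted. It names the source population, and each member must still pass screening. An active athlete without head contact in the last 3 months meets both criteria. The centre also covers weightlifting, so active does not always mean recent head contact.

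**Number of athletes concerned.** Athletes are 30/70 = 42.9% (Section 2.2) or 50/120 = 41.7% (Abstract), and half of the exposed participants (30/60 or 50/100). The active share is not given, so the number affected lies anywhere from 0 to 30, or 0 to 50.

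**If subconcussion counts.** With an assumed share a of athletes who are active with recent contact, n(1 − a) remain eligible:

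| a (assumed) | of 30 | of 50 |
|---|---|---|
| 25% | 22.5 | 37.5 |
| 50% | 15 | 25 |
| 75% | 7.5 | 12.5 |

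These count candidates from a fixed list. If recruitment continues until the group is full, the numbers need not fall.

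**If subconcussion does not count.** Assume a short-term rise of d SD in the recently exposed athletes and no chronic effect. The athlete-volunteer mean difference is (number exposed / n) × d. Rejection rates below are for a pooled two-sided t-test at 0.05, from 100,000 simulated trials with normal data and SD 1:

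| Groups | Exposed | d | Difference (SD) | Rejects |
|---|---|---|---|---|
| 50 v 20 | any | 0 | 0 | 5% |
| 50 v 20 | 25 | 0.2 | 25/50 × 0.2 = 0.10 | about 6.4% |
| 50 v 20 | 25 | 0.5 | 25/50 × 0.5 = 0.25 | about 14% |
| 50 v 20 | 38 | 0.8 | 38/50 × 0.8 = 0.608 | about 59% |
| 30 v 10 | any | 0 | 0 | 5% |
| 30 v 10 | 15 | 0.2 | 15/30 × 0.2 = 0.10 | about 5.8% |
| 30 v 10 | 15 | 0.5 | 15/30 × 0.5 = 0.25 | about 9.5% |
| 30 v 10 | 22 | 0.8 | 22/30 × 0.8 = 0.587 | about 31% |

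The span from no effect to a large one comes entirely from a and d, and the protocol gives neither. The Background links the classical markers to mild TBI and chronic TBI, not to subconcussion. The athlete-volunteer t-test is also an assumption: the stated aim is a diagnostic signature for TES, judged against a clinical TES reference standard. A comparison of TES classes within the exposed groups is disturbed only if recency of contact differs by class.

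**The case for a change.** The strongest case for a change is that eligibility belongs in the protocol and cannot be left to an analysis plan. Section 4.1 asks researchers to evaluate every criterion clearly, and with an undefined term they may not do so uniformly. If they take head injury narrowly, the date of last contact is not a required item, and asking for it after sampling brings recall error. The groups named in the protocol make recent contact foreseeable.

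That much stands: the term is undefined, the sentence lacks a comparator and a reference date, and nothing in the text settles either. Three things weaken the step to a change.
- The history item in Section 4.1 is open-ended, already asks for number, degree and time, and sits beside occupation, which may show whether an athlete is active. The record falls short only under the narrow reading, and detailed items usually sit in a case report form, which is not at hand.
- The obvious rewording, 3 months since the last mild TBI or concussion, would drop subconcussion from the clock. An athlete who qualifies on subconcussion alone would still have no date, and current contact would still be admitted.
- Separate reporting of active and retired athletes, or a repeat analysis in those without recent contact, is ordinary analysis-plan content.

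**Conclusion.** The point is a gap in definition that screeners and analysts can fill sensibly, not a design fault. With criterion 3 read as at least 3 months since the latest event of the kinds listed in criterion 2, the criteria, the athlete group and the screening history fit together. This reading is an inference from the order of the criteria and the chronic condition under study; the protocol does not state it. If the narrower reading was meant, the consequence is uncontrolled recent contact in an unknown part of the athlete group, which is 42% to 43% of participants.

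The protocol supports no figure for lost eligibility or for bias. The bias is nil if subconcussive contact does not raise the markers, and becomes large only with a high active share and a large rise, both assumed. For the novel primary markers, an effect is no more than plausible. The wording merits a clarifying line for screeners; it does not call for a change to the plan.
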